6.5. Data Cutoff Rule and Date

Analyses will be done when all patients have completed the final treatment visit.

6.6. Pooling of Centers

This is a multiple-center single dose treatment study. Given that the expected enrollment at any individual site is expected to be fewer than 3 patients, patients from all sites will be pooled together into a combined site in the analyses for the primary and secondary effectiveness endpoints. A site effect will be not examined because there will be too few patients within each center to provide an informative estimate of this effect.

•

6.7. Subgroups

Two subgroups based on age at dosing (study day 1) will be assessed in the selected analysis (developmental milestones and statistical modeling parts):

- Patients with age at dosing (study day 1) \leq 4 months (120 days)
- Patients with age at dosing (study day 1) $>$ 4 months (120 days).

7. DEMOGRAPHIC, OTHER BASELINE CHARACTERISTICS AND MEDICATION

7.1. Patient Disposition and Withdrawals

The number and percent of patients who are still in the study when all patients reach 14 and 18 months-of-age will be tabulated.

Among those who discontinued the study prior to reaching the 18 months-of-age visit, the distribution of reasons for discontinuation will be enumerated.

The number and percentage of screened patients who screen failed and the reasons for screen failure (inclusion/exclusion criteria, withdrew consent, and/or other) will be summarized in a table. A listing of reason for screen failure will be provided for all patients who screen failed.

Reasons for dose interruption will be presented in a listings if any.

This analysis will be conducted on the Safety Analysis Set.

7.2. Demographic Data

The age of the patient at the time of gene therapy infusion will be summarized. The distribution of patients by sex, ethnicity (Hispanic/Latino vs. Non-Hispanic/non-Latino), and race will be presented. Patient demographics will be summarized using the Safety Analysis Set.

Demographic data will be determined using the following calculations:

Age at Study day 1 = (Study day 1 visit date - date of birth + 1), expressed in days

Height/Length (in cm) = height (in inches) * 2.54

Weight (in kg) = weight (in lbs) * 0.4536

The following statistics regarding the patient's characteristics at birth will be summarized: gestational age (weeks), birth weight (kg), birth length (cm), and head circumference (cm).

The presence of significant medical conditions obtained from medical history will be summarized. In particular, the following parameters will be summarized regarding symptoms and history of Spinal Muscular Atrophy: age at symptom onset (if applicable), baseline SMA symptoms (if applicable), family history of SMA, and number of siblings affected by SMA.

Patient baseline characteristics will be summarized on the Safety Analysis Set.

7.3. Medical History and Concomitant Diseases

Medical history data will be summarized and presented using body systems and conditions/diagnoses as captured on the eCRF. The body systems will be presented in alphabetical order and the conditions/diagnoses will be presented in alphabetical order within each body system. The number and percentage of patients with a particular

condition/diagnosis will be summarized by overall. Patients reporting more than one condition/diagnosis within a body system will be counted only once for that body system.

7.4. Prior and Concomitant Medications

Prior and concomitant medications will be summarized by overall. A prior medication is defined as any medication taken prior to the date of the gene therapy infusion of study drug. A concomitant medication is defined as any medication that started prior to the date of the infusion of study drug and continued to be taken after the infusion of study drug or any medication that started on or after the date of the infusion of study drug. The number and percentage of patients taking prior or concomitant medications will be summarized by generic drug name based on the WHO Drug Dictionary.

7.4.1. Specific Medication Subgroups

In an attempt to reduce the host immune response to the AAV-based therapy, patients will receive prophylactic prednisolone (approximately 1 mg/kg/day) 24 hours prior to the gene transfer and continuing for approximately 30 days. After 30 days of treatment, the dose of prednisolone can be tapered for patients whose ALT values, AST values, and T-cell response are below the threshold of $\leq 2 \times$ ULN for ALT and AST, and < 100 SFC/ 10^6 PBMCs in accordance with the following treatment guideline:

- Weeks 5 and 6: 0.5 mg/kg/day
- Weeks 7 and 8: 0.25 mg/kg/day
- Week 9: prednisolone discontinued

The total number of days receiving prednisolone and total cumulative dose of prednisolone administered during the entire study (mg/kg) will be computed for each patient. Doses captured as volume (e.g., 5 mL QD) will be converted to mg/kg utilizing the patient's screening weight and known prednisolone solution concentration (25 mg/5 mL or 5 mg/mL).

To compute total cumulative dose, the total dosing period is subdivided into dosing intervals represented by constant dose levels. On the day of a dosage change, the entire day is represented under the new dosing interval at the new dose.

For example, consider a patient who receives 1.0 mg/kg of prednisolone for Day 1 to Day 20, then on Day 20, dose is elevated to 2.0 mg/kg until Day 30, at which point it is tapered to 1.5 mg/kg. On Day 35, the dose is lowered to 1.0 mg/kg and continues until Day 40 when it is lowered further to 0.5 mg/kg until all prednisolone dosing stops on Day 45. For this patient,

$$\begin{aligned}\text{Total Cumulative Dose} = & (1.0 \text{ mg/kg} \times 19 \text{ days}) + \\ & (2.0 \text{ mg/kg} \times 10 \text{ days}) + \\ & (1.5 \text{ mg/kg} \times 5 \text{ days}) + \\ & (1.0 \text{ mg/kg} \times 5 \text{ days}) + \\ & (0.5 \text{ mg/kg} \times 6 \text{ days}) = 54.5 \text{ mg/kg}\end{aligned}$$

Exposure will be summarized for the Safety Analysis Set.

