4.6.2. Vital Signs

Length, weight, blood pressure, respiratory rate, pulse, axillary temperature, and pulse oximetry will be collected at every visit. For detailed schedule of events table, see [Table 1](#).

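### Prednisolone doses recorded as volume are converted to mg/kg with one screening weight for the whole study, so cumulative exposure is misstated whenever an infant's weight changes; the stop-date count also needs stating

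*SAP*

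**What the plan says.** SAP Section 7.4.1 defines two exposure measures for the Safety Set: days on prednisolone, and a cumulative dose. On the second it says that the "total cumulative dose of prednisolone administered during the entire study (mg/kg) will be computed for each patient".

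The conversion rule covers only some records: "Doses captured as volume (e.g., 5 mL QD" and similar entries. These "will be converted to mg/kg utilizing the patient's screening weight and known prednisolone solution concentration (25 mg/5 mL or 5 mg/mL". No later weight is substituted at any point. Section 3.5 places screening on Days -30 to -2. Section 4.6.2 says: "Length, weight, blood pressure, respiratory rate, pulse, axillary temperature, and pulse oximetry will be collected at every visit". Table 1 also shows weight on Day -1.

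On counting days, Section 7.4.1 says: "On the day of a dosage change, the entire day is represented under the new dosing interval at the new dose". Its worked example has a patient on "1.0 mg/kg of prednisolone for Day 1 to Day 20, then on Day 20, dose is elevated to 2.0 mg/kg until Day 30", then on 1.5 mg/kg, with a step down to 1.0 mg/kg on Day 35. From Day 40 the example has the dose "lowered further to 0.5 mg/kg until all prednisolone dosing stops on Day 45". The printed total is 54.5 mg/kg, with six days in the last interval.

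**The concern.** The patients are infants under 180 days old at infusion, so body weight can change materially between screening and the end of a steroid course. A milligram amount given on a later day but divided by the screening weight is not the mg/kg received on that day. The error grows as the current weight moves away from the screening weight, so it is largest in infants treated longest.

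Duration is not random. Section 7.4.1 makes the taper after 30 days conditional on ALT, AST and T-cell response being below thresholds, so infants whose values stay raised can remain on prednisolone longer. Records already in mg/kg enter unconverted, so two infants dosed alike could show different totals because their sites recorded the dose differently.

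At stake is the accuracy of a safety exposure summary, which readers may set beside the hepatotoxicity summaries of Section 10.3.2.4. The stop-date question is smaller: it shifts the day count by one and the total by one day at the final dose.

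**Working it through.** **1. The worked example (inputs: Section 7.4.1).** With the printed day counts:

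19 × 1.0 + 10 × 2.0 + 5 × 1.5 + 5 × 1.0 + 6 × 0.5 = 19 + 20 + 7.5 + 5 + 3 = 54.5 mg/kg, over 45 days.

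The SAP's figure reproduces. The first four counts follow the change-day rule: Days 1–19, 20–29, 30–34 and 35–39. The last interval starts on Day 40.

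- Day 45 dosed: Days 40–45, 6 days, total 54.5 mg/kg over 45 days.
- Day 45 not dosed: Days 40–44, 5 days, total 51.5 + 2.5 = 54.0 mg/kg over 44 days.

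The difference is 0.5 mg/kg (0.5/54.0 = 0.9%) and one day. It does not grow with duration.

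**2. The fixed screening weight.** The SAP gives no weights, so the following are assumptions:

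- Weight changes linearly by a fraction g of screening weight per 30 days.
- Screening weight is taken s days before the course, with s = 2 or 30 (the ends of the window). Elapsed time on Day t is taken as t + s; one day more or less moves the results by at most 0.5 percentage point.
- The volume is adjusted to current weight, so the true daily dose d(t) follows the guideline in Section 7.4.1: 1.0 mg/kg on Days 1–30, then 14 days at 0.5 and 14 days at 0.25.
- All doses are recorded as volume.

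Reported dose on Day t = d(t) × [1 + g(t + s)/30]. Summing over the course:

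reported/true − 1 = g × (m + s)/30, where m = Σ d(t)·t / Σ d(t) is the dose-weighted mean day.

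*Guideline course.* Σ d = 30 + 7 + 3.5 = 40.5 mg/kg. Σ d·t = 465 + 262.5 + 180.25 = 907.75. So m = 22.4.

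*Starting dose 60 days longer (an assumption, to show the effect of duration).* Σ d = 90 + 7 + 3.5 = 100.5 mg/kg. Σ d·t = 4095 + 682.5 + 390.25 = 5167.75. So m = 51.4.

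| Course | s | g = −5% | g = 0 | g = +5% | g = +15% |
|---|---|---|---|---|---|
| Guideline, 40.5 mg/kg | 2 | −4.1% | 0 | +4.1% | +12.2% |
| Guideline, 40.5 mg/kg | 30 | −8.7% | 0 | +8.7% | +26.2% |
| 60 days longer, 100.5 mg/kg | 2 | −8.9% | 0 | +8.9% | +26.7% |
| 60 days longer, 100.5 mg/kg | 30 | −13.6% | 0 | +13.6% | +40.7% |

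At the extremes, a true 40.5 mg/kg would be reported as 42.1 to 51.1 mg/kg, and a true 100.5 as 109.4 to 141.4 mg/kg.

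If volumes are instead set from the screening weight and not adjusted for growth, the percentages barely move: +4.0% to +25.8% on the guideline course and +8.7% to +39.1% on the longer one.

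**The case against.** The strongest reply is that the reach is narrow. The rule applies only to volume records, and the SAP does not say how common they are. Overstatement needs weight gain, which cannot be assumed for every infant: Section 8.2.1 makes weight maintenance part of a co-secondary endpoint. The result is a descriptive summary in a single-arm study of up to 20 patients, no readable section relates prednisolone dose to liver outcomes, and days on prednisolone do not depend on weight. All of this stands and limits the importance. It does not rescue the rule, which gives a wrong mg/kg value whenever weight changes, while better weights are already collected.

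A reader might infer several stronger points that the SAP does not support:

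- *The worked example breaks its own rule.* The rule concerns a change to a new dose. A stop has no new dose, and 54.5 mg/kg is correct if Day 45 is the last dosed day. This is an ambiguity, not a demonstrated breach.
- *The concentration is wrong.* The two expressions are one strength written in two ways.
- *The 5 mL example implies a 25 kg infant.* It illustrates how a record may look, not a planned dose.
- *Counting omits the pre-infusion dose.* The example that starts on Day 1 is hypothetical, and the rule covers the entire study.
- *Using Day -1 weight for AVXS-101 contradicts the screening weight.* That weight defines the dose of another product.
- *The overstatement reaches 39% to 61%.* This needs a 4 kg infant gaining 30 g/day (22.5% per 30 days) and weighed on Day -30: 22.5% × 52.4/30 = 39%, or 22.5% × 81.4/30 = 61% with 60 more days. It is a corner case.

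**Conclusion.** The concern holds for the conversion weight. Section 7.4.1 fixes one screening weight for all volume-recorded prednisolone. For infants who gain weight this overstates their cumulative mg/kg, increasingly with time on the drug. Under an assumed gain of 5% to 15% of screening weight per 30 days, the size is about 4% to 26% on the guideline course and 9% to 41% with 60 more days at the starting dose. Those ranges assume that all doses are recorded as volume; a patient with mixed records would be affected less. There is no error without weight change, and the sign reverses with weight loss.

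The stop date is a separate gap in definition, worth 0.5 mg/kg and one day in the SAP's example.

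Neither point touches a tested endpoint. The SAP should be corrected, but no efficacy conclusion depends on it.

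**What to change.** In Section 7.4.1, replace the screening weight with the most recent recorded weight on or before the start of each volume-recorded dosing interval, using the Day -1 weight for the first. Where one volume runs unchanged across several visits, say whether the interval is split at each new weight; otherwise drift within a long interval remains.

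State whether the stop date counts as a dosed day, apply this to both the cumulative dose and the number of days on prednisolone, and align the example: 54.5 mg/kg over 45 days if Day 45 is dosed, 54.0 mg/kg over 44 days if it is not.

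The cost is a few lines of SAP text and a programmed look-up of weights already collected. No new data are needed, and no treatment changes.

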7.4.2. Other Therapies

Non-medication Therapies/Procedures will be defined as “Prior” and/or “Concomitant”. Prior Non-medication Therapies/Procedures are defined as therapies or procedures started prior to injection of AVXS-101. Concomitant Non-medication Therapies/Procedures are defined as therapies or procedures ongoing at time of injection of AVXS-101 or started after the injection.

Non-medication Therapies/Procedures will not be summarized. A listing will be provided.

8. EFFICACY

8.1. Primary Efficacy Endpoints and Analysis

8.1.1. Co-Primary Efficacy Endpoint: Functional Independent Sitting at 18 months of age

An independent expert reviewer will evaluate recorded videos of CHOP-INTEND or Bayley Scales assessments conducted at clinic visits. The reviewer will judge whether the video reveals evidence of the milestone achievement of functional independent sitting [REDACTED].

During the Screening visit, the physical therapist will complete an assessment of baseline milestone achievement, including functional independent sitting; this assessment must address all milestones/items noted in [Appendix 21.1](#) that are at or below the child's expected function for age. Items that are below the child's expected function for age that are not successfully achieved during the baseline evaluation should be repeated at subsequent visits until successfully performed.

The milestones of sitting independently (Bayley Scales gross motor subtests item 22 and 26) will be assessed at every subsequent visit regardless of starting point on the scale. These milestones will also be assessed at the 18 months of age visit, regardless of previous attainment, as the Bayley Scales do not necessarily require the child to repeat previously attained milestones.

The number and percent of patients whom, through video evidence, exhibit the milestone achievement of independent sitting for at least 30 seconds at 18 months of age study visit will be summarized for the ITT population. Potential missing values will be imputed per [Section 6.3](#). A one-sided Exact Binomial Test will be used to test the null hypothesis of $p=0.1\%$ at significance level of 0.025. Furthermore, the corresponding 97.5% confidence intervals will be estimated by the exact method for binomial proportions.

In case for the presence of missing value, sensitivity analyses outlined in [Section 6.3](#) will be carried out to evaluate the appropriateness of assumptions for the missing data.

Additionally, for patients who achieve the functional independent sitting at 18 months of age visit, the age at which the subjects first achieved independent sitting for 30 seconds will be summarized.

8.1.2. Co-Primary Efficacy Endpoint: Avoidance of Death or Surrogate for Death (Permanent Ventilation)

The co-primary efficacy endpoint is defined by avoidance of the combined endpoint of either (a) death or (b) permanent ventilation, defined as requirement of tracheostomy or ≥ 16 hours of respiratory assistance per day (includes non-invasive ventilatory support) continuously for ≥ 14 days in the absence of an acute reversible illness, excluding perioperative ventilation. Permanent ventilation, so defined, is considered a surrogate for death.

Non-invasive ventilatory support usage data will be extracted directly from each patient's device; the data will be downloaded from the device's SD card through software provided by the

manufacturer and transferred as an external dataset. Each patient will also be assessed by investigator whether permanent ventilation criteria has been met, which is the primary endpoint. If the permanent ventilation criteria are met, the event (surrogate for death) will be reported in [REDACTED] system for primary efficacy analysis.

An “acute reversible illness” is defined as any condition other than spinal muscular atrophy that results in increased medical intervention (i.e., increased requirement for external ventilator support; use of other concomitant meds as rescue) requirements and is expected to be reversible or improved following definitive intervention (i.e., surgery, antibiotics) or introduction of escalated supportive care, such as hospitalization (i.e., for upper respiratory infection, spontaneous fracture). The specific duration of the condition antecedent intervention shall not be considered in the definition of “acute”. The date of “definitive intervention” shall be defined as the date of provision of a procedure (i.e., surgery, etc.) or medication (i.e., antibiotics) intended to cure or substantially improve the condition. For conditions, such as viral respiratory infections, for which supportive care is provided, the date of “definitive intervention” shall be considered the date of hospitalization or substantial escalation of care.

“Perioperative” use reflects any alteration of ventilator use related to a surgical or other medical procedure of any nature for which the participant received medications that could impair or interfere with respiratory function.

For a participant who develops an acute reversible illness and/or requires perioperative ventilator support, a recovery period not to exceed 21 days following the date of definitive intervention will be instituted. Following this recovery period, the condition will be considered sub-acute and the participant will become evaluable with regards to the surrogate survival endpoint (Requirement of ventilator support of ≥ 16 hours/day for greater than 14 days).

Example: Using this approach it would mean that on day 1, patient A receives definitive intervention for an acute reversible illness resulting in ventilator support for ≥ 16 hours/day. Days 1-21 will be provided to permit recovery from the acute reversible illness. On Day 22, the participant is no longer considered to have an acute illness. Should the participant continue to require ≥ 16 hours/day of ventilator support from day 22 to day 36, he or she shall be considered to meet the surrogate endpoint.

Statistical approach: The proportion surviving event-free to 14 months of age will be computed in the ITT population. Patients who terminate the study prior to reaching 14 months of age for any reason will be considered treatment failures (event).

As a comparator, in a natural history study of SMA Type 1 patients, [Finkel et al \(2014\)](#) estimated that only 25% of SMA Type 1 patients with 2 copies of *SMN2* would survive event-free to 13.6 months of age.

The observed proportion surviving in the current study will be compared to the natural history data [\(5\)](#) of the matching cohort using a two-sample Fisher’s exact test, along with the corresponding 95% confidence intervals.

If status at 14 months of age is coded using variable SURVIVE as 1 if patient survived to 14 months of age without requiring permanent ventilation, and 2 otherwise, then the SAS code to generate the endpoint analysis is:

```
proc format;  
value survive  
1= 'Yes'  
2= 'No'  
;  
Value grp  
1='AVXS'  
2='PNCR'  
;  
run;  
proc freq data=x order=data;  
table grp*survive / measures riskdiff;  
exact fisher / alpha=0.05;  
run;
```

Time to death or permanent ventilation through 14 months of age is an additional sensitivity analysis. In case if there is at least 1 patient who is event-free, but discontinue study prior to his/her 14 month birthday, a sensitivity analysis, based on the approach for time to event, will be carried out. In this analysis, time to event will be censored at 14 months of age or at the date of discontinuation. The survival rate at 14 months of age will be estimated by Kaplan-Meier method, and survival curves for AVXS treated patients and the PNCR cohort will be compared using log-rank test at significance level of 0.05.

Additionally, the proportion of patients who experience each of the following events by 14 months of age will be summarized:

- Death
- Permanent ventilation

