Based upon preliminary results from the ongoing Phase 1 clinical study AVXS-101-CL-101, at least 80% of treated symptomatic patients with bi-allelic *SMN1* deletions and 2 copies of *SMN2* without the *SMN2* gene modifier mutation (c.859G>C) are expected to achieve the co-primary efficacy endpoint of survival through 14 months of age. It is anticipated that 75% of patients in the PNCR [5] population would not survive beyond 13.6 months of age, and that these control patients will represent a 25% survival rate based upon the natural history of the disease. With this efficacy, an enrolled sample size of 15 patients that meet ITT criteria (assuming 30% of patients are excluded from the analysis) would provide power of >80% to detect a significant difference with $\alpha = 0.05$ using a two sample 2-sided Fisher's exact test, comparing to patient-level data drawn from a published natural history observational study dataset with patients who meet the eligibility criteria for this study (bi-allelic *SMN1* deletions, 2 copies of *SMN2*, age of onset ≤ 6 months of age). The natural history observational study dataset was collected by PNCR network from the study performed at three large, tertiary care centers in the United States (Harvard University, Columbia University, Children's Hospital of Philadelphia; PNCR).

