5.5. PNCR Control Population

The PNCR Natural History dataset ([Finkel, 2014](#)) is drawn from a large natural history study performed on a large cohort of 337 patients with any form of spinal muscular atrophy followed at 3 large, internationally recognized tertiary medical centers with significant expertise in the management of SMA (Harvard University/Boston Children's Hospital, Columbia University and the University of Pennsylvania/Children's Hospital of Philadelphia). Previously identified patients followed in PNCR site clinics and newly diagnosed patients were enrolled. All eligible patients were offered participation in the PNCR study. Study visits were scheduled at baseline and at 2, 4, 6, 9, and 12 months and every 6 months thereafter. The SMA standard of care guidelines published in 2007 were used as a basis for providing uniform care among the study sites. For purposes of this study, sitting (for SMA Type 2) was defined as being able to sit independently for >10 seconds;

children who were unable at any point to achieve this milestone were classified as SMA Type 1.

A natural history control population is drawn from the PNCR Natural History Dataset ([Finkel, 2014](#)) consisting of all patients with age of onset \leq 6 months, bi-allelic deletion of *SMN1* (exon 7/8 common homozygous deletion) and 2 copies of *SMN2* for whom enrollment data (retrospective and prospective) is available to determine survival based on the defined criteria. The *SMN2* modifier mutation (c.859G>C) described by Prior and colleagues (Prior, Thomas W., et. al. "A positive modifier of spinal muscular atrophy in the *SMN2* gene." *The American Journal of Human Genetics* 85.3 (2009): 408-413.) was not assessed in the PNCR study cohort. Based on these criteria, 23 patients from the PNCR dataset are included in the control population. Among them, 17 patients reached the combined endpoint of death or the need for a minimum of 16 hours/day of noninvasive ventilation support for a minimum of 14 continuous days by 13.6 month of age. The survival rate at 13.6 months of age is approximately 25% (17/23), of which the control cohort will be used as comparator with ITT population for survival analysis.

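### The survival co-primary's illness exemption has no limit before intervention, and section 6.2.4.1 and the stated control definition omit it; reconcile the sections and add a sensitivity test

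*SAP*

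**What the plan says.** Section 8.1.2 of the SAP scores permanent ventilation as an event: tracheostomy, or support for at least 16 hours a day over at least 14 days without a break. Ventilation during an acute reversible illness or around a procedure is left out. Sections 1.2, 3.1 and 4.1.1 carry the same exclusion. Four parts of 8.1.2 matter here.

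- **Before the intervention.** On what makes a condition acute: "The specific duration of the condition antecedent intervention shall not be considered in the definition of" acute. No maximum is given.
- **Start of the clock.** This is the date of the procedure or drug meant to cure or substantially improve the condition. For illnesses managed by supportive care, it "shall be considered the date of hospitalization or substantial escalation of care".
- **After the intervention.** Here "a recovery period not to exceed 21 days following the date of definitive intervention will be instituted". The condition then becomes sub-acute and the child is evaluable again.
- **The count.** The definition asks for 14 days or more. The recovery-period paragraph asks for more than 14, and its example runs from day 22 to day 36, which is 15 days inclusive.

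Two other sections describe the event without the exclusion. Section 6.2.4.1 derives it as death, tracheostomy, or non-invasive support of 16 or more hours a day for 14 or more days. Section 5.5 says that "23 patients from the PNCR dataset are included in the control population" and that 17 of them had the event by 13.6 months. It describes that event as death or the same ventilation threshold, and mentions neither an illness exclusion nor a recovery period.

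**The concern.** The exemption can only remove events. Whether it applies turns on judgements made at the site: that a condition other than SMA explains the ventilation, that it is expected to reverse or improve, and on what date the definitive intervention fell. Section 8.1.2 has the investigator assess whether the criteria are met, and section 3.8 makes the study open-label.

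A treated child with several weeks at 16 or more hours a day, attributed to an illness, could therefore be event-free under 8.1.2 and an event under 6.2.4.1 as written. A control with the same record would be an event under 5.5 as written. The sensitivity analysis in 8.1.2 deals with children who leave early and does not touch this. Under section 8.4 the survival test is also the gate to both co-secondary endpoints.

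**Working it through.** **Inputs.** Fisher's exact test, two-sided 0.05; 80% event-free if treated and 25% in controls; 15 children with 30% excluded, so 15 × 0.70 = 10.5, taken as 10 or 11 (section 3.7). Controls 23 with 17 events, so 6/23 = 26.1% event-free (5.5). Landmark at 420 days of age (6.2.3). Recovery period of 21 days (8.1.2).

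**1. The plan's own power figure.** Sum Bin(x; n, 0.80) × Bin(y; 23, 0.25) over all outcomes with Fisher p ≤ 0.05 in favour of treatment. This gives 0.824 for n = 10 and 0.846 for n = 11. The stated power above 80% reproduces. The issue is the endpoint definition, not the sample size.

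**2. Longest continuous run without an event.** With one recovery period and nothing exempt before it: 21 + 13 = 34 days (35 if 15 counted days are needed). With L exempt days before the intervention: L + 34.

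| L | Days without an event |
|---|---|
| 0 | 34 |
| 14 | 48 |
| 28 | 62 |
| 60 | 94 |

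The text sets no maximum for L. If a new illness or procedure opened a second period just before the count completed, and the count reset, the run could reach 2 × 34 = 68 days (70 on the 15-day reading). The SAP neither allows nor rules this out.

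**3. Effect at the landmark.** With the intervention on age day D, days D to D+20 are exempt and counting starts on D+21.

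- 14 counted days: the last is D+34. D + 34 ≤ 420 requires D ≤ 386, so from day 387 the criterion cannot be completed in time.
- 15 counted days, as in the SAP's example: the last is D+35, which requires D ≤ 385, so the limit is day 386.

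This assumes that the illness is held to cover any earlier part of the run. If the criterion was met before the illness, the event already stands. For comparison, with no exemption a run starting on day s reaches 14 days on s+13, so runs starting from day 408 are already too late. The exemption moves that edge forward by 408 − 387 = 21 days.

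**4. Sensitivity of the test.** The SAP gives no number of affected children, so the shift is an assumption. Start from about 80% event-free and move children one at a time to the event column, against 6/23:

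| Analysed | Start | 1 moved | 2 moved | 3 moved | 4 moved |
|---|---|---|---|---|---|
| 10 | 8/10, p = 0.007 | 7/10, 0.026 | 6/10, 0.114 | – | – |
| 11 | 9/11, p = 0.003 | 8/11, 0.023 | 7/11, 0.060 | – | – |
| 15 | 12/15, p = 0.002 | 11/15, 0.007 | 10/15, 0.020 | 9/15, 0.049 | 8/15, 0.168 |

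Two reclassified children remove significance at 10 or 11, and four at 15.

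**The case against.** Much of the case against is sound.

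- **Repeated restarts.** A reader might infer that each new escalation reopens 21 days, so that the event can be put off indefinitely. For the same condition 8.1.2 rules this out: the period may not exceed 21 days and the condition is then sub-acute. Only a distinct illness or procedure in the same run is left open.
- **A long run before the landmark.** Take 16 hours a day from day 360 and an intervention on day 387. Exemption runs to day 407 and the 14th counted day is 421, so the child is event-free at day 420 after 420 − 360 + 1 = 61 days. That holds only if the illness is accepted as covering days 360 to 386 and the clock does not start earlier. In a supportively treated illness, the move to 16 hours may itself be the escalation. Counting then starts on day 381 and the criterion is met on day 394 or 395, an event. With no illness accepted, the 14th day is 373, also an event. The open period therefore matters mainly where a curative procedure or drug comes late.
- **Late interventions.** One might infer that a child with an intervention from day 387 cannot have an event at all. Death, tracheostomy and a criterion met before the illness all still count.
- **Controls.** Section 5.5 selects children whose data allow survival to be determined on the defined criteria. An exclusion may have been applied to them. Its one-line event description states none, but a difference in practice is not established.
- **Visibility.** Sections 6.2.4.1 and 10.11 already tabulate ventilation by category and by hours, so heavy use would often show. They do not link it to the event-free classification or to the test.

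The exclusion is also deliberate and forms part of the primary objective in 3.1. Counting illness days retrospectively would change the endpoint, not clarify it.

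**Conclusion.** The concern holds as a gap and an inconsistency in the endpoint definition. The exemption has no stated limit before the definitive intervention. Section 8.1.2 does not say how successive distinct illnesses or procedures, or a run in progress on day 420, are classified, and it gives two day counts. Section 6.2.4.1 omits the exemption and 5.5 states none, so treated and control children may not be scored alike. Any resulting error favours treatment.

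The size is conditional. From the planned 80% it takes two reclassified children at 10 or 11 analysed, or four at 15, to lose significance. A reader might infer that a single child decides the result. That is so only at the edge of significance, for example 9/15 (p = 0.049) against 8/15 (0.168); from 12/15 one child moves p only from 0.002 to 0.007. Nor do the documents support saying that the endpoint no longer measures permanent ventilation: nothing in them shows that even one child is affected. The protocol, not seen here, may contain adjudication rules.

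**What to change.** Leave the illness and perioperative exclusion in the primary analysis, and before database lock:

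1. Reconcile sections 6.2.4.1 and 8.1.2 on whether the exclusion applies, and the two statements of the day count within 8.1.2.
2. State in 8.1.2 how a second, distinct illness or procedure in one continuous run is handled, including whether the count resets, and how a run in progress on day 420 is classified.
3. List every treated child whose event-free status at 14 months depends on the exemption, with the dates of the run, the illness or procedure, and the intervention.
4. Pre-specify a sensitivity Fisher test that scores those children as events, which matches the control definition in 5.5 as written.

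The cost is SAP wording, one listing and one extra analysis, which may show a slightly lower survival rate. Device data may be incomplete: section 4.6.10 makes card data conditional on the machine used, and 6.2.4.1 allows parent report for use before screening. The listing should therefore give the source of the hours for each child.
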